Note: The denominator for the calculation of the percentage is the number of AEs with non-missing severity with the given preferred term or in the given system organ class. Adverse events that are definitely, probably, or possibly related, or for which the relationship is missing, are considered related.

Table 9.5

OPIOID USE RELATED TREATMENT EMERGENT ADVERSE EVENTS: INCIDENCE BY SYSTEM ORGAN CLASS AND PREFERRED TERM (SUBJECT LEVEL)  
SAFETY POPULATION

System Organ Class/Preferred Term	Iovera (N=xx) n (%)	Standard of Care (N=xx) n (%)
System Organ Class 1	xx (xx.x)	xx (xx.x)
Preferred Term 1	xx (xx.x)	xx (xx.x)
Preferred Term 2	xx (xx.x)	xx (xx.x)
...		
System Organ Class 2	xx (xx.x)	xx (xx.x)
Preferred Term 1	xx (xx.x)	xx (xx.x)
Preferred Term 2	xx (xx.x)	xx (xx.x)
...		

Program Name: Creation date, time

Source: Listing 2.1

Note: The denominator for the calculation of the percentage is N, the number of subjects in the treatment group, and the numerator is the number of subjects with at least one AE in that system organ class or with that preferred term. Adverse events that are definitely, probably, or possibly related, or for which the relationship is missing, are considered related.

Table 9.6

OPIOID USE RELATED TREATMENT EMERGENT ADVERSE EVENTS BY SYSTEM ORGAN CLASS/PREFERRED TERM AND SEVERITY (EVENT LEVEL)  
SAFETY POPULATION

Iovera (N=xx)

System Organ Class/Preferred Term	Mild	Moderate	Severe	Total with Non-Missing Severity	
	n (%)	n (%)	n (%)	n (100%)	n
Any Adverse Event	xx (xx.x)	xx (xx.x)	xx (xx.x)	xx (100.0)	xx
System Organ Class 1	xx (xx.x)	xx (xx.x)	xx (xx.x)	xx (100.0)	xx
Preferred Term 1	xx (xx.x)	xx (xx.x)	xx (xx.x)	xx (100.0)	xx
Preferred Term 2	xx (xx.x)	xx (xx.x)	xx (xx.x)	xx (100.0)	xx
...					

Program Name:

Creation date, time

Source: Listing 2.1

Note: The denominator for the calculation of the percentage is the number of AEs with non-missing severity with the given preferred term or in the given system organ class. Adverse events that are definitely, probably, or possibly related, or for which the relationship is missing, are considered related.

[Note: This table will be continued for Standard of Care.]

[figure not shown]

Table 11

SUBJECT SATISFACTION  
ITT POPULATION

[figure not shown]
Visit	Variable	Statistic	Iovera (N=xx)	Standard of Care (N=xx)
Week 6	Overall knee pain status since the beginning of the study			
	Very much worse	n (%)	xx (xx.x)	xx (xx.x)
	Much worse	n (%)	xx (xx.x)	xx (xx.x)
	Minimally worse	n (%)	xx (xx.x)	xx (xx.x)
	No change	n (%)	xx (xx.x)	xx (xx.x)
	Minimally improved	n (%)	xx (xx.x)	xx (xx.x)
	Much improved	n (%)	xx (xx.x)	xx (xx.x)
	Very much improved	n (%)	xx (xx.x)	xx (xx.x)
	Overall knee pain status since the beginning of the study (1)	n Mean Median SD Minimum - Maximum	xx x.x x.x x.x x - x	xx x.x x.x x.x x - x
	Subject satisfaction with pain management following surgery (2)	n Mean Median SD Minimum - Maximum	xx x.x x.x x.x x - x	xx x.x x.x x.x x - x
Week 12	...	...	...	...

[figure not shown]
Program Name:

Creation date, time

(1) Very much worse=-3, Much worse=-2, Minimally worse=-1, No change=0, Minimally improved=1, Much improved=2, Very much improved=3.

(2) Measured on a scale of 0 to 10, with 0 being very unsatisfied and 10 being very satisfied.

[figure not shown]

Table 15

STUDY EXIT  
ITT POPULATION

Variable	Iovera (N=xx) n (%)	Standard of Care (N=xx) n (%)
Primary Reason Off Study		
Completed all visits	xx (xx.x)	xx (xx.x)
AE/SAE	xx (xx.x)	xx (xx.x)
Lost to follow-up	xx (xx.x)	xx (xx.x)
Non-compliant participant	xx (xx.x)	xx (xx.x)
Withdrew consent	xx (xx.x)	xx (xx.x)
Death	xx (xx.x)	xx (xx.x)
Investigator decision	xx (xx.x)	xx (xx.x)
Medical need for prohibited medications or treatment	xx (xx.x)	xx (xx.x)
Other	xx (xx.x)	xx (xx.x)
Did subject exit with unresolved adverse events?		
Yes	xx (xx.x)	xx (xx.x)
No	xx (xx.x)	xx (xx.x)

Program Name:  
Source: Listing 1

Creation date, time

Table 16

PROTOCOL DEVIATIONS  
ITT POPULATION

Type of Protocol Deviation	Iovera (N=xx) n (%)	Standard of Care (N=xx) n (%)
Any Protocol Deviation	xx (xx.x)	xx (xx.x)
Subject consent not obtained prior to study procedures	xx (xx.x)	xx (xx.x)
Eligibility criteria not met	xx (xx.x)	xx (xx.x)
Pre-treatment assessment not complete	xx (xx.x)	xx (xx.x)
Iovera Treatment not complete	xx (xx.x)	xx (xx.x)
TKA surgery deviation	xx (xx.x)	xx (xx.x)
Anesthesia/analgesia deviation	xx (xx.x)	xx (xx.x)
Post-treatment/follow-up assessment not complete	xx (xx.x)	xx (xx.x)
Follow-up out of window	xx (xx.x)	xx (xx.x)
Follow-up visit not done	xx (xx.x)	xx (xx.x)
Other: Incorrect Prescription (1)		
Other: reason	xx (xx.x)	xx (xx.x)

Program Name:

Creation date, time

Source: Listing 3

Note: A subject can have more than one type of protocol deviation, so the percentages may sum to more than 100%.

(1) Includes deviations due to patients not taking Tramadol.

*Programming note: for 'Other' category, please append specific reason. There will likely be several 'Other' rows.*

Listing 1

STUDY EXIT  
ITT POPULATION

Treatment Group	Subject Number	Safety Population?	Per-Protocol Population?	Incorrect Opioid Prescription?			Primary Reason Off Study	Did subject exit with unresolved adverse events?	Comments
xxxxxxxxx	xxx	xxx	xxx	xxx	yyyy-mm-dd (xx)	xxxxxxxxx		xxx	xxxxxxxxx
xxxxxxxxx	xxx	xxx	xxx	xxx	yyyy-mm-dd (xx)	Other, specify		xxx	xxxxxxxxx

---

Program Name:

Creation date, time

Note: Study day is relative to day of TKA (Day 0).

*Programming note: footnote any subjects where randomized and actual treatment group differ.*

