8.4 Risks

The iovera[°] device involves percutaneous access to subcutaneous tissue using a needle and use of dermal anesthesia. Passage of a needle into the skin, cooling of subcutaneous soft tissue and delivery of local anesthesia are known to be associated with the following risks:

- Bruising (ecchymosis)
- Swelling (edema)
- Inflammation and/or redness (erythema)
- Pain and/or tenderness along the treatment line
- Altered sensation (localized dysesthesia)

Proper use of the device as described in the *User Guide* can help reduce or prevent the following complications:

[figure not shown]
- Injury to the skin related to application of cold or heat
- Hyper- or hypo-pigmentation at the treatment site
- Skin dimpling at the treatment site
- Loss of motor function outside the target area

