10.4.4 Safety

Adverse events (AEs) will be coded using the Medical Dictionary for Regulatory Activities (MedDRA). Treatment-emergent AEs (TEAEs) are adverse events with onset after study treatment begins and that are not present at baseline or, if present at baseline, have worsened in severity. For AEs with missing start dates, the AE will be considered treatment-emergent unless there is additional information indicating that the AE started prior to study treatment. Only treatment emergent AEs will be summarized.

The number and percentage of subjects with at least one TEAE, at least one device-related TEAE, at least one serious TEAE, at least one serious adverse device effect, at least one unanticipated serious adverse device effect, at least one anticipated serious adverse device effect, and at least one TEAE leading to study withdrawal will be presented by treatment group. AEs that are definitely, probably, or possibly related to the device, or for which the relationship to the device is missing, will be considered device-related. TEAEs will be summarized at the subject level by MedDRA system organ class (SOC) and preferred term using frequencies and percentages. TEAEs will also be tabulated at the event level by severity and by relationship to the device for each treatment group.

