## **9.0 SAFETY ANALYSES**

All adverse event analyses will be performed on the Safety Population.

The summary of AEs will be limited to treatment emergent AEs. For AEs with a missing start date, the AE will be considered treatment emergent unless there is additional information indicating that the AE started prior to study treatment.

Adverse events (AEs) will be coded using the Medical Dictionary for Regulatory Activities (MedDRA). Treatment-emergent AEs (TEAEs) are defined as any adverse event with onset on or after study treatment begins or any adverse event already present at baseline that worsens in severity. For AEs with missing start dates, the AE will be considered treatment-emergent unless there is additional information indicating that the AE started prior to study treatment. Only treatment emergent AEs will be summarized.

The number and percentage of subjects with at least one TEAE, at least one iovera procedure-related TEAE, at least one iovera device-related TEAE, at least one opioid use related TEAE, at least one serious TEAE, and at least one TEAE leading to study withdrawal will be presented by treatment group. AEs that are definitely, probably, or possibly related, or for which the relationship is missing, will be considered related.

The number and percentage of subjects having a TEAE in each System Organ Class (SOC) and having each individual type of adverse event (Preferred Term) will be presented. TEAEs will also be summarized at the event level by SOC/Preferred Term and severity. This will be done for all TEAEs, iovera procedure related TEAEs, iovera device related TEAEs, and opioid use related TEAEs.

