		95% CI for Mean (1)	(xx.x, xx.x)	(xx.x, xx.x)	
	72 Hours Post-op to 2 Weeks Post-op	n	xx	xx	
		Mean	xx.x	xx.x	xx.x (xx.x, xx.x)
		Median	xx.x	xx.x	
		SD	xx.x	xx.x	
		Minimum - Maximum	xx - xx	xx - xx	
		95% CI for Mean (1)	(xx.x, xx.x)	(xx.x, xx.x)	
	2 Weeks Post-op to 6 Weeks Post-op	...	...	...	...
	6 Weeks Post-op to 12 Weeks Post-op	...	...	...	...
	Hospital Discharge to 2 Weeks Post-op	n	xx	xx	
		Mean	xx.x	xx.x	xx.x (xx.x, xx.x)
		Median	xx.x	xx.x	
		SD	xx.x	xx.x	
		Minimum - Maximum	xx - xx	xx - xx	
		95% CI for Mean (1)	(xx.x, xx.x)	(xx.x, xx.x)	
	Hospital Discharge to 6 Weeks Post-op	p-value (2)			x.xxxx
		...	...	...	...
		...	...	...	...

Program Name:

Creation date, time

Source: Listing 4

Note: Missing pill count data were imputed using multiple imputation methods.

(1) Confidence interval based on the t-distribution.

(2) p-value from a one-sided, two sample t-test, testing the null hypothesis that the true iovera mean is greater than or equal to the true Standard of Care mean versus the alternative hypothesis that the true iovera mean is less than the true Standard of Care mean.

Table 6.1 will be repeated in the following tables:

Table 6.2

OPIOID CONSUMPTION: TOTAL DAILY MORPHINE EQUIVALENT (TME):  
EXCLUDES DISCONTINUATIONS DUE TO ADVERSE EVENTS  
ITT POPULATION

Table 7.1

OPIOID CONSUMPTION: TOTAL DAILY MORPHINE EQUIVALENT (TME)  
PER PROTOCOL POPULATION

Table 7.2

OPIOID CONSUMPTION: TOTAL DAILY MORPHINE EQUIVALENT (TME):  
EXCLUDES DISCONTINUATIONS DUE TO ADVERSE EVENTS  
PER PROTOCOL POPULATION

*Programming note: for Tables 6.2 and 7.2, please add Listing 2.1 to Source.*

Table 8.1

TREATMENT EMERGENT ADVERSE EVENTS (TEAEs): OVERVIEW (SUBJECT LEVEL)  
SAFETY POPULATION

Parameter	OCS (N=xx) n (%)	Standard of Care (N=xx) n (%)
At least one TEAE	xx (xx.x)	xx (xx.x)
At least one iovera procedure-related TEAE (1)	xx (xx.x)	-
At least one iovera device-related TEAE (1)	xx (xx.x)	-
At least one opioid use related TEAE (1)	xx (xx.x)	xx (xx.x)
At least one serious TEAE	xx (xx.x)	xx (xx.x)
At least one TEAE leading to study withdrawal	xx (xx.x)	xx (xx.x)

Program Name:

Creation date, time:

Source: Listing 2.1

Note: Percentages are calculated based on the number of subjects in the ITT Population.

(1) Adverse events that are definitely, probably, or possibly related, or for which the relationship is missing, are considered related.

Table 8.2

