TREATMENT EMERGENT ADVERSE EVENTS: INCIDENCE BY SYSTEM ORGAN CLASS AND PREFERRED TERM (SUBJECT LEVEL)  
SAFETY POPULATION

System Organ Class/Preferred Term	Iovera (N=xx) n (%)	Standard of Care (N=xx) n (%)
System Organ Class 1	xx (xx.x)	xx (xx.x)
Preferred Term 1	xx (xx.x)	xx (xx.x)
Preferred Term 2	xx (xx.x)	xx (xx.x)
...		
System Organ Class 2	xx (xx.x)	xx (xx.x)
Preferred Term 1	xx (xx.x)	xx (xx.x)
Preferred Term 2	xx (xx.x)	xx (xx.x)
...		

Program Name: Creation date, time  
Source: Listing 2.1  
Note: The denominator for the calculation of the percentage is N, the number of subjects in the treatment group, and the numerator is the number of subjects with at least one AE in that system organ class or with that preferred term.

Table 8.3

TREATMENT EMERGENT ADVERSE EVENTS BY SYSTEM ORGAN CLASS/PREFERRED TERM AND SEVERITY (EVENT LEVEL)  
SAFETY POPULATION

Iovera (N=xx)

System Organ Class/Preferred Term	Mild	Moderate	Severe	Total with Non-Missing Severity	
	n (%)	n (%)	n (%)	n (100%)	n
Any Adverse Event	xx (xx.x)	xx (xx.x)	xx (xx.x)	xx (100.0)	xx
System Organ Class 1	xx (xx.x)	xx (xx.x)	xx (xx.x)	xx (100.0)	xx
Preferred Term 1	xx (xx.x)	xx (xx.x)	xx (xx.x)	xx (100.0)	xx
Preferred Term 2	xx (xx.x)	xx (xx.x)	xx (xx.x)	xx (100.0)	xx
...					

Program Name:

Creation date, time

Source: Listing 2.1

Note: The denominator for the calculation of the percentage is the number of AEs with non-missing severity with the given preferred term or in the given system organ class.

[Note: This table will be continued for Standard of Care.]

Table 9.1

IOVERA PROCEDURE RELATED TREATMENT EMERGENT ADVERSE EVENTS: INCIDENCE BY SYSTEM ORGAN CLASS AND PREFERRED TERM (SUBJECT LEVEL)  
SAFETY POPULATION

System Organ Class/Preferred Term	Iovera (N=xx) n (%)
System Organ Class 1	xx (xx.x)
Preferred Term 1	xx (xx.x)
Preferred Term 2	xx (xx.x)
...	
System Organ Class 2	xx (xx.x)
Preferred Term 1	xx (xx.x)
Preferred Term 2	xx (xx.x)
...	

Program Name:

Creation date, time

Source: Listing 2.1

Note: The denominator for the calculation of the percentage is N, the number of subjects in the treatment group, and the numerator is the number of subjects with at least one AE in that system organ class or with that preferred term. Adverse events that are definitely, probably, or possibly related, or for which the relationship is missing, are considered related.

Table 9.2

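### No summary table counts subjects with a severe TEAE by arm, and the event-share percentage in Table 8.3 moves with each arm's number of non-severe events

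*SAP*

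**What the plan says.** Protocol 10.4.4 states that "TEAEs will also be tabulated at the event level by severity and by relationship to the device for each treatment group". SAP 9.0 carries this forward: "TEAEs will also be summarized at the event level by SOC/Preferred Term and severity".

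The shells follow that text. Table 8.3 (all TEAEs, iovera, then continued for standard of care) gives n (%) of events as mild, moderate and severe. Its note reads "The denominator for the calculation of the percentage is the number of AEs with non-missing severity"; this is set separately for each row of the table. Tables 9.2, 9.4 and 9.6 use the same rule for procedure-related, device-related and opioid-related events.

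The subject-level tables are 8.1, 8.2, 9.1, 9.3 and 9.5. None is split by severity. In Table 8.2 the denominator is the arm's N and "the numerator is the number of subjects with at least one AE in that system organ class or with that preferred term". The nearest row in Table 8.1 is "At least one serious TEAE".

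Protocol 8.4 lists local reactions known to follow the needle, the cold and the local anaesthetic, among them "Pain and/or tenderness along the treatment line". It gives no rate and no grade for any of them.

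**The concern.** The usual safety question is what proportion of subjects in each arm had a severe event. The planned tables do not answer it. They give the number of severe events and their share of all events in the arm.

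That share has a denominator that is itself an outcome. The control arm receives neither iovera nor a sham (Protocol 9.4), so it cannot have reactions to the procedure. In the iovera arm, the treatment areas are checked for adverse events straight after the session (Protocol 9.5). Non-severe local reactions recorded as adverse events would enlarge the iovera denominator and lower its severe percentage, although no severe event was avoided. A reader who compares the two percentages could then draw the wrong conclusion about severe harm. Even a reader who uses the counts could not tell one subject with several severe events from several subjects with one each.

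**Working it through.** **1. Is there a subject-level severity summary?** There is none.

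| SAP table | Level | Severity shown | Arms |
|---|---|---|---|
| 8.1 | subject | no (serious only) | both |
| 8.2 | subject | no | both |
| 8.3 | event | yes, % of events | both |
| 9.1, 9.3 | subject | no | iovera only |
| 9.2, 9.4 | event | yes, % of events | iovera only |
| 9.5 | subject | no | both |
| 9.6 | event | yes, % of events | both |

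**2. Does serious stand in for severe?** No. Protocol 11.2 defines serious by outcomes such as death or hospitalisation. Protocol Table 3 defines severe by considerable interference with usual activities. A severe but non-serious event does not enter the serious row of Table 8.1.

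**3. What does an event count leave open?** Assume 12 severe events in an arm of about 60 subjects (Protocol 10.1). They could have occurred in anything from 1 subject (1/60 = 1.7%) to 12 subjects (12/60 = 20.0%).

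**4. How does the event share behave?** The shells hold only placeholders, so there is no stated figure to reproduce. All event counts below are assumptions. Let s be severe events, B background events per arm (including the s severe ones) and m extra non-severe local events in the iovera arm.

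- Standard of care: severe share = s / B
- iovera: severe share = s / (B + m)
- Subject level, if each severe event is in a different subject: s / N

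With s = 6 and N = 60, the subject-level figure is 6/60 = 10.0% in both arms throughout.

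| B | Standard of care | iovera, m = 15 | m = 30 | m = 60 |
|---|---|---|---|---|
| 60 | 6/60 = 10.0% | 6/75 = 8.0% | 6/90 = 6.7% | 6/120 = 5.0% |
| 120 | 6/120 = 5.0% | 6/135 = 4.4% | 6/150 = 4.0% | 6/180 = 3.3% |

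**5. Can the share hide a real difference?** Keep B = 60 in standard of care, of which 54 events are non-severe. Give iovera the same 54 non-severe background events, 12 severe events in 12 subjects, and m = 60. The shares are 12/(54 + 12 + 60) = 12/126 = 9.5% for iovera and 6/60 = 10.0% for standard of care. By subject, the figures are 12/60 = 20.0% and 6/60 = 10.0%. The printed counts, 12 and 6, would still show the excess of events.

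**6. Can it go the other way?** Yes. If iovera had 15 fewer non-severe background events and no local reactions recorded, its share would be 6/(60 − 15) = 6/45 = 13.3% against 10.0%, again with severe harm unchanged.

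**7. Which rows are affected?** Denominators are set per row. The local-reaction effect reaches the all-events row of Table 8.3 and any system organ class row that contains such reactions. Rows for unrelated preferred terms are untouched.

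**The case against.** The strongest reply is that Table 8.3 is a description of events, as Protocol 10.4.4 specifies, and should be read as one. Several parts of this stand.

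- Severity is not shown only as a share. Every cell prints the event count, with N in the header.
- No difference, interval or test of the severe percentage is planned, so no specified analysis is biased.
- Tables 9.2 and 9.4 have no control arm. Table 9.6 concerns opioid-related events, which local reactions would not normally enter unless opioid relatedness is missing.
- The number and grade of local reactions are unknown. Protocol 9.7 names anticipated observations alongside adverse events and does not say whether they enter the adverse event tables.
- Background events need not be equal. The trial expects less opioid use with iovera, which could mean fewer non-severe opioid-related events there. Permitted local infiltration also differs between arms (Protocol 9.6).
- Listing 2.1 shows severity by subject, so a subject count could be made by hand.

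The reply does not supply the missing summary. A listing is not a by-arm table, and an event count is not a subject count. Protocol 10.4.4 asks for event-level tabulation but does not rule out a subject-level one, and SAP Table 8.2 already uses the arm's N as denominator.

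**Conclusion.** The point holds as a reporting gap. No summary table gives subjects with a severe TEAE by arm; this follows from the shells and needs no assumption. The event-share percentage in parts of Table 8.3 depends on each arm's number of non-severe events; this follows from the denominator rule.

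The size does rest on assumptions. With 6 severe events and 60 or 120 background events per arm, 15 to 60 extra non-severe local events move iovera's share from 10.0% to 8.0%–5.0%, or from 5.0% to 4.4%–3.3%.

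A reader might infer that the plan biases the severity comparison in favour of the device, or that an excess of severe events would be hidden. The documents do not support either. They give no event counts or grades, the net direction could reverse, no formal comparison is planned, and the severe counts are printed. Nor does the bias argument extend to all four severity tables. No endpoint, test or sample size is affected.

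**What to change.** - Add the row 'At least one severe TEAE' to Table 8.1 and to the list of subject-level summaries in SAP 9.0.
- Add to Table 8.3 the number and percentage of subjects by maximum severity, with the arm's Safety Population N as denominator. Table 9.6 could optionally have the same.
- The event counts may stay. Tables 9.2 and 9.4 need no change on the dilution argument.
- When editing Table 8.1, settle its denominator: the title names the Safety Population, but the note bases percentages on the ITT Population.

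The cost is SAP wording, shell edits and slightly longer tables. Severity per event and subject is already in Listing 2.1, so no new data are needed.

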**Listing 2.1**

**ADVERSE EVENTS (AEs)**

**SAFETY POPULATION**

**Part 1 of 3**

Treatment Group	Subject Number	Event	Event Description	System Organ Class	Preferred Term	Event Start Date (Study Day)	Event Window
xxxxxxxxxx	xxx	xxxxxxxxxx	xxxxxxxxxxxx	xxxxxxxxxxxx	xxxxxxxxxxxx	yyyyy-mm-dd (xx)	xxxxxxxxxx

---

Program Name:

Creation date, time

Note: Study day is relative to day of TKA (Day 0).

**Listing 2.1**

**ADVERSE EVENTS (AEs)**  
**SAFETY POPULATION**  
**Part 2 of 3**

Treatment Group	Subject Number	Event	Severity	Reported as SAE? (#1)	If 'Yes' in #1, Reason	Action(s) Taken	Study Exit due to this AE?
XXXXXXXX	XXX	XXXXXXXXXX	XXXXXXXX	XXX	XXXXXXXXXX	XXXX, XXXXXX	XXX

---

Program Name:

Creation date, time

**Listing 2.1**

**ADVERSE EVENTS (AEs)**

**SAFETY POPULATION**

**Part 3 of 3**

Treatment Group	Subject Number	Event	Relatedness			If 'Possible', 'Probable', or 'Definite' in #1, Pre-Existing Condition
			To Iovera Procedure	To Iovera Device	To Pre-Existing Condition (#1)	
xxxxxxxxx	xxx	xxxxxx	xxxxxxxx	xxxxxxxxx	xxxxxxxx	xxxxxxxxxxxx

---

Program Name:

Creation date, time

**Listing 2.2**

**ADVERSE EVENT STATUS  
SAFETY POPULATION**

Treatment Group	Subject Number	Event	Event Start Date (Study Day)	Visit	Status	Outcome at Completion of Study (#1)	If 'Resolved' in #1, Date Resolved (Study Day)
xxxxxxxxx	xxx	xxxxxxx	yyyy-mm-dd (xx)	Treatment Visit Day of TKA 72-Hours Post-op 2 Weeks Post-op 6 weeks Post-op 12 Weeks Post-op Other	xxxxxx	xxxxxxx	yyyy-mm-dd (xx)

---

Program Name:

Creation date, time

Note: Study day is relative to day of TKA (Day 0).

Listing 3

PROTOCOL DEVIATIONS  
ITT POPULATION

Treatment Group	Subject Number	Deviation ID	When did deviation occur?	Deviation Type	Reason for Deviation	Clinically Significant?
xxxxxxxx	xxx	xx	xxxxxxxx Other, specify	xxxxxxxxxxxxxx Pre-treatment assessment not complete, specify	xxxxxxxx Other, explain	xxx
			Follow-up Visit, specify	Iovera® treatment not complete, specify		
				TKA surgery deviation, specify		
				Anesthesia/analgesia deviation, specify		
				Post-treatment/Follow-up assessment not complete, specify		
				Follow-up visit not done, specify		
				Incorrect prescription (1)		
				Other, explain		

---

Program Name:

Creation date, time

(1) Incorrect prescription is included in the Other category in the CRF. Includes deviations due to patients not taking Tramadol.

Listing 4

OPIOID ACCOUNTABILITY AND PILL COUNT  
ITT POPULATION

Treatment Group	Subject Number	Visit	Medication Name	Strength (Dosage)	Morphine Equivalent	If prescription filled or re-filled, number of new tabs acquired since last visit	Number of tabs re-dispensed at last visit	Number of tabs counted (remaining) at this visit	Total Daily Morphine Equivalent (TME) [1]	Notes/ Discrepancies
XXXXXXXX	XXX	XXXXX	XXXXXXXXXXXXXX	XXXXXX	XXXX	XX None	XX None	XX	XXX	XXXXXXXXXX

---

Program Name:

Creation date, time

Note: Calculated relative to TKA. The cumulative morphine equivalent will be divided by the number of days to provide the Total Daily Morphine Equivalent (TME) for the subject as of the visit.
